#### **6.7. Secondary objective 4**

*To compare the rates of treatment failure and recurrence of the intervention and control arm.*

This will be done by calculating the proportion of participants who do not have a negative culture result at end of treatment or who relapse post treatment in each of the two arms. The proportions will be compared these using the chi-square test or the Fisher's exact test.

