### **2.2 Secondary Objectives**

- 2.2.1 To determine the time to culture-conversion of the Moxifloxacin regimen and the Ethambutol regimen using data from 2-, 4-, 6-, and 8-week cultures
- 2.2.2 To compare the proportion of patients with any Grade 3 or 4 adverse reactions
- 2.2.3 To compare adverse events and 2-month culture conversion rates among HIV-infected patients vs. HIV-uninfected patients
- 2.2.4 To compare the rates of treatment failure and recurrence of the Intervention and Control arm.
- 2.2.5 To compare TB cure rates at month 6 and at end of TB treatment between the Intervention and Control Arm

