## **Outcome status**

### *Definition of treatment failure:*

Patient whose baseline smear (or culture) was positive and remains or becomes positive again at 5 months or later during treatment. This definition excludes those patients who are diagnosed with RR-TB or MDR-TB during treatment.

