##### Intention-to-treat population

This population consists of all participants enrolled and randomised to the intervention and control arms. Individuals who will be identified as ineligible for enrolment based on criteria pre-randomisation criteria will be excluded. Moreover, individuals with no post-randomisation visit and no data collected will be excluded.

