## 5. GENERAL STATISTICAL ISSUES

All tests will be two-sided, and the significance level will be 0.05.

Outliers will be identified by looking at summary statistics and scatter plots. All outliers detected will be verified from the source documentation. Outliers that have biologically impossible values will be excluded from all data summaries and analyses. If one (or several) outlier(s) change(s) the interpretation of the data substantially, two summaries and analyses will be done, one with and one without the outlier(s).

If a participant has missing data at a specific time point, data at all non-missing time points for the participant will be used and included in the summaries. Missing data will be ignored (i.e. treated as missing at random) unless patterns are identified which would potentially bias analysis results.

Where applicable, analyses will be stratified by HIV status.

All statistical analyses will be done using SAS (SAS Institute Inc., Cary) version 9.4 or higher.

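### SAP 6.7 does not measure treatment failure as the protocol defines it, leaves missing end-of-treatment cultures unresolved, and plans one pooled proportion where the objective asks for two rates

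*SAP*

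**What the plan says.** Protocol 2.2 sets the objective: "To compare the rates of treatment failure and recurrence of the Intervention and Control arm". SAP 1.2 repeats it.

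The protocol's outcome definitions describe a failure as a "Patient whose baseline smear (or culture) was positive and remains or becomes positive again at 5 months or later during treatment" and add: "This definition excludes those patients who are diagnosed with RR-TB or MDR-TB during treatment".

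SAP 6.7 puts the objective into practice by "calculating the proportion of participants who do not have a negative culture result at end of treatment or who relapse post treatment" in each arm, compared by a chi-square or Fisher's exact test. No other SAP section compares failure or recurrence. Neither document defines relapse or recurrence.

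Two general SAP provisions bear on who is counted. Section 5 says "Missing data will be ignored (i.e. treated as missing at random) unless patterns are identified which would potentially bias analysis results". The intention-to-treat definition in section 4 removes those found ineligible on pre-randomisation criteria and adds that "individuals with no post-randomisation visit and no data collected will be excluded".

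The protocol section on withdrawal from the study ends follow-up, apart from safety, for patients withdrawn because the initial isolate is MDR-TB or the initial cultures are negative.

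**The concern.** The protocol's failure is a positive finding, whereas the SAP's event is the absence of a negative one. The two differ for every participant with no usable end-of-treatment culture. They also differ for anyone whose result changes between month 5 and the end of an extended course. A failure rate reported from SAP 6.7 would therefore not be the rate that the protocol promises.

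The handling of a missing culture is left open. Section 6.7 read alone makes it an event, and section 5 applied first removes it. Two competent analysts could report different numbers. In an open-label trial that choice should be fixed before the data are seen.

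The objective names two outcomes with different timing and different populations at risk. A single pooled proportion answers neither question separately.

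**Working it through.** **The plan's own figure.** Protocol 9.1 gives N = 330 for 75% v 60%, two-sided 0.05, 80% power, with a continuity-corrected chi-square test. Uncorrected, n0 = [1.960·√(2·0.675·0.325) + 0.842·√(0.75·0.25 + 0.60·0.40)]² / 0.15² ≈ 151.9 per arm. Corrected, n = (n0/4)·[1 + √(1 + 4/(0.15·n0))]² ≈ 164.9, so 165 per arm and 330 in total. The figure reproduces and does not depend on this point. No size or power is stated for secondary objective 4.

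**The definitions side by side.**

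| Participant | Protocol failure | SAP 6.7 read literally |
|---|---|---|
| Culture positive at end of treatment (month 5 or later) | Yes | Event |
| Missing or contaminated end-of-treatment culture, no positive at month 5 or later | No | Event |
| Death or loss, no positive at month 5 or later | No | Event |
| RR-TB or MDR-TB diagnosed during treatment, no negative end-of-treatment culture | Excluded | Event |
| Withdrawn for initial MDR-TB or negative initial culture, not followed | No | Event, if kept in the ITT set |
| Positive at month 5, treatment extended, culture negative at its end | Yes | Not an event (unless relapse) |
| Smear positive at month 5 or later, culture negative at end | Yes | Not an event (unless relapse) |

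On the withdrawn groups, the ITT definition names neither. The inclusion criteria require a positive smear, not a positive culture, so a negative initial culture does not make a participant ineligible.

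**Illustration of size.** The documents give no failure, relapse or missing rates for this trial, so all inputs here are assumptions:
- failure f = 5% among those assessed;
- relapse r = 8% among those with a negative end-of-treatment culture;
- missing share m = 5-20%. The 12% treatment-interruption rate in Protocol 1.1 lies in this range, but it is a national figure for a regimen that neither arm uses and is not a missing-culture rate.

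The literal proportion is P = m + (1 − m)·[f + (1 − f)·r]. The bracket is 0.05 + 0.95·0.08 = 0.126.
- m = 5%: P = 0.05 + 0.95·0.126 = 17.0%; missing share of events 0.05/0.170 = 29%.
- m = 12%: P = 0.12 + 0.88·0.126 = 23.1%; missing share 52%.
- m = 20%: P = 0.20 + 0.80·0.126 = 30.1%; missing share 66%.

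With r = 12% instead, P is 21-33% and the missing share 24-60%.

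**Dilution when missingness is equal.** Take the failure component alone, with true failure 5% v 2.5% (risk ratio 0.50). At m = 12% the literal figures are 0.12 + 0.88·0.05 = 16.4% and 0.12 + 0.88·0.025 = 14.2%, a ratio of 0.87. At m = 5% the ratio is 0.76, and at m = 20% it is 0.92. With 165 control participants and 12% missing, about 7 failures (165·0.88·0.05) become about 27 events (165·0.164).

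**Unequal missingness, no true difference** (f = 5%, r = 8% in both arms, 165 per arm). Rejection probability = Φ[(d − 1.96·se0)/se1], where se0 uses the pooled and se1 the separate variances.
- Missing 8% v 14%: P = 19.6% v 24.8%, d = 0.0524, se0 = 0.0458, se1 = 0.0457; rejection about 21%.
- Missing 10% v 20%: P = 21.3% v 30.1%, d = 0.0874, se0 = 0.0481, se1 = 0.0479; rejection about 44%.

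At r = 12% these become about 18% and 39%. With equal missingness the test keeps its 5% level.

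**Pooling.** Suppose failure is 10% v 4% and relapse among the rest is 4% v 10%. The pooled figures are 0.10 + 0.90·0.04 = 13.6% and 0.04 + 0.96·0.10 = 13.6%, so two opposite effects disappear.

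**The case against.** The strongest defence is that SAP 5 is a general rule that can be applied before 6.7. The proportion is then taken among participants with an end-of-treatment result, and no conflict remains. That reading is available. A reader might infer a flat contradiction between sections 5 and 6.7, but the documents do not support one, and section 5 also carries its own exception for patterns that could bias the results. What stands is that 6.7 does not say which reading governs. Even the softer reading leaves the mismatch with the protocol definition for extended treatment, the smear route and the RR/MDR exclusion.

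The protocol also limits missing sputum. It provides for induction when a good spontaneous specimen cannot be produced, a dedicated end-of-treatment visit, and text messages to those who miss appointments. No passage suggests that missingness will differ by arm. This is fair: the 8% v 14% and 10% v 20% gaps are assumptions, and the rejection figures come entirely from them.

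Counting missing as failure is a legitimate rule for a composite of unfavourable outcome. The fault is to use it unlabelled for an outcome that the protocol defines otherwise.

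Finally, pooling breaches neither the failure definition nor section 5. It departs only from the objective's wording. Nothing bars component counts from being tabulated, and SAP 6.8 compares cure separately. But cure is a different outcome, and no separate comparison of failure or of recurrence is planned.

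**Conclusion.** The point holds for this secondary endpoint. Followed as written, SAP 6.7 would not produce the protocol's failure rate. It adds participants without a bacteriological failure and drops some who have one. It leaves the missing-data rule to the analyst, and it does not provide the two rates named in the objective.

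The mismatch of definitions rests on the text alone. The size rests on the assumed 5% failure, 8% relapse and 5-20% missing: a literal proportion of 17-30%, with 29-66% of events being missing results.

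A reader might infer that the result would mostly reflect attendance and sputum availability. That is not established. At 8% relapse the missing share passes one half only near 12% missing, and the true rates are unknown. Nor does the rule inflate type I error in itself. With equal missingness it dilutes a real failure contrast, and false positives of about 21% or 44% arise only under the assumed gaps between arms.

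The primary analysis and N = 330 are unaffected.

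**What to change.** In SAP 6.7:

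1. Define failure as the protocol does, with the month-5 rule, the smear and culture routes, and the RR-TB/MDR-TB exclusion.
2. Report failure and recurrence as two separate comparisons. Define recurrence and its denominator, for example participants who completed treatment without failure.
3. State how missing or contaminated cultures, deaths, losses, and withdrawals for initial MDR-TB or negative initial cultures are handled, and whether SAP 5 applies.
4. Keep any pooled or missing-as-failure measure only as a composite labelled as such, or as a sensitivity analysis.
5. Tabulate by arm the number without an end-of-treatment culture, with reasons.

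The cost is SAP wording, one new definition and a few extra table rows. No new data collection and no change in sample size are needed.

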#### **6.8. Secondary objective 5**

*To compare TB cure rates at month 6 and at end of TB treatment between the Intervention and Control Arm*

This will be achieved by calculating the proportion cured at month 6 and at the end of treatment in each of the two arms and comparing these proportions using the chi-square test or Fisher's exact test.

